Food and Drug Administration 2003, Grady, Sawaya et al. 2009). Participants will be asked to record each hot flash they experience on this diary and rate it as: 1) mild (sensation of heat without sweating), 2) moderate (sensation of heat with sweating, not preventing the participant from continuing with activity), or 3) severe (sensation of heat with sweating, causing cessation of activity); severity definitions will be provided with the diary.

For this study in which the average frequency of hot flashes at baseline will be high (i.e., at least 7 hot flashes per 24-hour period), the study team believes that this type of real-time diary will lead to more accurate assessment of hot flash frequency than alternate diary formats in which subjects only record their hot flashes once or twice a day by retrospectively recalling their hot flashes over the past 12 or 24 hours. To avoid diary fatigue, participants will be asked to complete the diary for a 7-day period before the baseline, 5-week, and 12-week visits only, rather than recording their hot flashes continuously throughout the trial. To facilitate real-time recording, the diary has been designed to be small and portable, so that women can carry it with them throughout the day and keep it at their bedside at night.

In addition to assessing change in frequency of any hot flashes, diary data will be used to assess change in frequency of moderate-to-severe hot flashes as an important secondary outcome. A total hot flash severity score will also be calculated by taking the sum of severity ratings for all hot flashes recorded during each 7-day period.

G.1.2 Other symptom and quality-of-life outcomes (at the screening, 5-week, and 12-week visits)

Additional symptom and quality-of-life outcomes will be assessed using several validated, self-administered, structured-item questionnaires, including:

A. The Hot Flash Related Daily Interference Scale (HFRDIS)

The HFRDIS is a 10-item self-administered questionnaire that assesses the degree to which hot flashes have interfered with participants' activities over the prior week. Interference with each activity is rated on a 10-point scale, and an overall score is calculated as the average of the items. The HFRDIS has been shown to have good internal consistency reliability, construct validity, and sensitivity to change (Carpenter 2001)

B. The Pittsburgh Sleep Quality Index (PSQI) and Pittsburgh Sleep Diary

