In the event that a participant develops a potentially severe adverse event such as chest pain during weaning, she will be directed to seek immediate emergency attention, just as she would during any other time point of the study. Although all study medication will be stopped while the participant receives emergency care, it should be possible to manage any side effects safely in the emergency care setting regardless of medication discontinuation.

Study coordinators will also try to schedule and complete a post-discontinuation telephone call that will occur at least 28 days after discontinuation of study medication, to promote appropriate monitoring of adverse events following discontinuation of study drug.

K. STATISTICAL CONSIDERATIONS

K.1 General Design Issues

A randomized, parallel-group, placebo-controlled trial design has been selected to examine the following aims and test the following hypotheses related to the efficacy, safety, and tolerability of transdermal NTG for treatment of menopausal hot flashes:

Objective 1: Determine the efficacy of uninterrupted transdermal NTG therapy in reducing the frequency of hot flashes in peri- and postmenopausal women.

Hypothesis 1: Compared to placebo, uninterrupted use of NTG will result in at least a 20% greater decrease in the frequency of hot flashes (measured by validated symptom diaries) over 12 weeks.

Objective 2: To evaluate the efficacy of uninterrupted transdermal NTG therapy in reducing the severity of hot flashes in peri- and postmenopausal women.

Hypothesis 2: Compared to placebo, uninterrupted use of NTG will result in significant improvements in frequency of moderate-to-severe hot flashes and in cumulative hot flash severity score (assessed by validated symptom diaries) over 12 weeks.

Objective 3: Evaluate the efficacy of uninterrupted transdermal NTG therapy in improving other symptom- and quality-of-life outcome associated with hot flashes in peri- and postmenopausal women.

Hypothesis 3: Compared to placebo, uninterrupted use of NTG will result in significant improvements in hot flash-related sleep quality, anxiety and depression, and menopause-related quality of life over 12 weeks.

Objective 4: Examine the tolerability and safety of uninterrupted transdermal NTG therapy in peri- and postmenopausal women with hot flashes.

Hypothesis 4: Compared to placebo, uninterrupted use of NTG will be associated with higher rates of mild

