headache during the first 24 hours of therapy, but no significant differences in rates of chest pain, syncope, or severe adverse events defined by CTCAE severity grade 3 or higher.

K.2 Data Analyses

K.2.1 Analyses for Objective 1

Analyses to address aim 1 will examine change in average daily hot flash frequency from baseline to 4 and 12 weeks of treatment, measured over 7 days by validated hot flash diaries (Sloan, Loprinzi et al. 2001, Food and Drug Administration 2003). The effect of NTG therapy will be estimated using linear mixed models (LMMs) for the repeated changes, adjusting for baseline values, under the assumption of an approximately constant treatment effects at 4 and 12 weeks; in supplementary analysis we will assess evidence for differences in the treatment effects at these two time points. The distribution of the LMM residuals will be assessed using Q-Q plots, and outcomes will be transformed if necessary to achieve approximate normality. Analyses will be by intention to treat, according to treatment assignment, and without regard to adherence.

K.2.2 Analyses for Objective 2

For additional confirmation of treatment effects on frequency of any hot flashes, we will also assess treatment effects on moderate-to-severe hot flashes and on total hot flash severity scores as secondary outcomes, also assessed by diary, using the same methods. The distribution of the LMM residuals will again be assessed using Q-Q plots, and outcomes will be transformed if necessary to achieve approximate normality. Analyses will again be by intention to treat, according to treatment assignment, and without regard to adherence.

K.2.3 Analyses for Objective 3

Analyses to address aim 2 will examine changes in sleep quality and duration, anxiety and depressive symptoms, and menopausal quality-of-life from baseline to 4 and 12 weeks. These outcomes will be captured by scores on validated self-administered questionnaires, with supplementation by sleep diary in the case of sleep duration. Intervention effects on these outcomes will be estimated using LMMs, adjusted for baseline scores. Approximate normality of the residuals will be checked using Q-Q plots, and outcomes will be transformed if necessary. Analyses will once again be by intention to treat and without regard to adherence.

K.2.4 Analyses for Objective 4

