Under these assumptions, a sample size of 140 (70 per group) should provide an estimated 87% power in 2-sided tests with type-I error of 5% to detect an 20% greater reduction in hot flash frequency (or 1.8 hot flashes per day) in the active treatment arm relative to the control arm. This will correspond to a 50-55% decrease in hot flash frequency from baseline in the active treatment group, which has previously been described as a clinically important effect in prior hot flash research (Butt, Deng et al. 2007). Estimates account for correlation of the repeated measures and loss to follow-up of up to 15%, and indicate that power will remain $\geq 80\%$ even if actual effect size or other parameters are less favorable than expected. This sample of 70 per group will also provide $>80\%$ power in 2-sided tests with type-I error of 5% to detect a between-group difference in mean frequency of moderate-to-severe hot flashes of ~ 1.5 hot flashes per day, as well as ~ 3.3 points in hot flash severity scores.

K.4 Additional Statistical Considerations

K.4.1 Drop-out rates

Based on past experience, participant dropout levels are expected to remain under 15% over 12 weeks. The assumption of non-informative dropout will be examined by comparing the baseline characteristics and early post-randomization outcomes of participants who are lost to follow-up versus retained in the study. If drop-out rates differ substantially between groups, analyses will be adjusted for baseline covariates associated with retention. In sensitivity analyses, we will also use multiple imputation of missing outcomes under plausible informative missingness assumptions, along with standard methods for calculating summary estimates and confidence intervals, to assess the potential impact of loss to follow-up on treatment effect estimates (Schafer 1999).

K.4.2 Dose effects

In the event that an overall treatment benefit is detected over 12 weeks, we will conduct exploratory analyses to probe for differences in the magnitude of treatment effects by highest-achieved NTG dose, by testing for interaction between treatment assignment and highest-achieved NTG dose in a linear mixed model for change in hot flash frequency. This analysis will control for the main effect of highest achieved dose to control the placebo effect of this self-selected variable, as well as baseline factors that may confound it, such as age, body mass index, and baseline hot flash frequency or severity.

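### Objective 2 is worded as a severity question, but both its endpoints mix frequency with severity and cannot tell a severity effect from a frequency effect

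*Combined protocol and SAP*

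**What the plan says.** - **Objective.** Section B.2 (item A) and section K.1 set a separate objective on severity: "Objective 2: To evaluate the efficacy of uninterrupted transdermal NTG therapy in reducing the severity of hot flashes". Frequency is Objective 1.
- **Endpoints.** Hypothesis 2 in K.1 looks for "significant improvements in frequency of moderate-to-severe hot flashes and in cumulative hot flash severity score". No other endpoint is attached to this objective.
- **Definition of the score.** Under G.1.1, women "record each hot flash they experience on this diary and rate it as: 1) mild", moderate (2) or severe (3). The total score is "calculated by taking the sum of severity ratings for all hot flashes recorded during each 7-day period". It is not divided by the number of flashes.
- **Analysis.** K.2.2 opens: "For additional confirmation of treatment effects on frequency of any hot flashes, we will also assess treatment effects on moderate-to-severe hot flashes", and on the total score, by the same baseline-adjusted mixed model as the primary outcome. There is no adjustment for total flash frequency.
- **Power.** K.3 claims more than 80% power for a difference of about 1.5 moderate-to-severe flashes per day and about 3.3 "points in hot flash severity scores". No time unit is attached to the score.

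The plan contains no mean rating per flash and no proportion moderate-to-severe, although every flash is rated. The Hot Flash Related Daily Interference Scale measures interference with activities and is not an Objective 2 endpoint.

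**The concern.** Each endpoint is a product of frequency and severity. The total score is the number of flashes times the mean rating. The moderate-to-severe count is the number of flashes times the share rated 2 or 3. A treatment that only prevents flashes, with the remaining ones just as severe as before, lowers both.

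At stake is the conclusion drawn for Objective 2. A significant result on either endpoint could come from fewer flashes, milder flashes or both, and no planned analysis says which. The wording of Objective 2 points to a severity conclusion, while K.2.2 describes the same analyses as "For additional confirmation of treatment effects on frequency of any hot flashes". The two passages need to be reconciled.

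**Working it through.** **1. The plan's own power figure.** K.3 states 87% power for 1.8 flashes/day with 70 per group, two-sided 5%, up to 15% loss, SD about 4.5 and correlation about 0.55.
- Retained per arm: 70 × 0.85 = 59.5.
- SD of the mean of two follow-ups, adjusted for baseline: 4.5 × √((1 + r)/2 − 0.55²). The correlation r between the two follow-ups is not stated.
- Assuming r = 0.55, the SD is 4.5 × √0.4725 = 3.09 and power is 88.8%. With r = 0.60, power is 87.1%.

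The figure reproduces, and nothing here disputes the sample size.

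**2. Inputs for a pure frequency effect.**
- From K.3: baseline 9/day, control reduction 3/day, effect 1.8/day. Follow-up is then 6.0/day on placebo and 4.2/day on active.
- From the pilot in C.3: 10.6 flashes/day at baseline, 7.2 of them moderate-to-severe, so the share s = 7.2/10.6 = 0.68.
- Assumption: the same severity mix in both arms.

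**3. Effect on the moderate-to-severe count.** 1.8 × 0.68 = 1.22/day.

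**4. Effect on the total score.** The split between moderate and severe is not given. If none of the moderate-to-severe flashes is severe, the mean rating is 1 + s = 1.68. If all are severe, it is 1 + 2s = 2.36.
- Score difference: 1.8 × 1.68 = 3.0 to 1.8 × 2.36 = 4.2 points/day, or 21 to 30 points over 7 days.
- Difference in mean rating per flash: 0.

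**5. Comparison with K.3.** 3.3/1.8 = 1.83, which lies inside the range 1.68 to 2.36. The detectable score difference is therefore about what the planned frequency effect produces by itself. This reads the 3.3 points per day. Over a 7-day sum, 1.8 fewer flashes a day removes at least 7 × 1.8 × 1 = 12.6 points, so a weekly reading fits poorly.

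**6. Sensitivity to the share (assumed values).**

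| Share s | Count, per day | Score, points/day |
|---|---|---|
| 4/7 = 57% (ratio of the two entry thresholds in E.2) | 1.03 | 1.8 × 1.57 = 2.8 to 1.8 × 2.14 = 3.9 |
| 68% (pilot) | 1.22 | 3.0 to 4.2 |
| 80% | 1.44 | 1.8 × 1.80 = 3.2 to 1.8 × 2.60 = 4.7 |

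**7. Illustrative simulation.** 2000 trials were simulated with 60 women per arm, one follow-up, baseline-adjusted regression, an assumed mix of 32/45/23% mild/moderate/severe in both arms, assumed between-woman variability and a frequency effect only. The result was p < 0.05 in 91% for frequency, 90% for the total score, 88% for the moderate-to-severe count and 4.7% for mean rating per flash.

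**8. The pilot.** With an unchanged mix, the fall from 10.6 to 5.0 flashes/day would take the moderate-to-severe count from 7.2 to 7.2 × 5.0/10.6 = 3.4. It fell to 2.3. Of the drop of 4.9, 3.8 (78%) is what frequency alone would give. The share went from 68% to 2.3/5.0 = 46%, which hints at milder flashes in a small single-arm study.

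**The case against.** Several points on the other side stand.

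- **The endpoints are not blind to severity.** A reader might infer that they would miss a real severity effect. They would not. If severe flashes became moderate, the score would fall; if moderate became mild, both endpoints would fall. They lack specificity, not sensitivity.
- **The plan does not say it will report a severity benefit.** Hypothesis 2 names the two measures literally, G.1.1 defines the score openly as a sum, and K.2.2 calls them confirmation of frequency. A misleading claim is a risk created by the objective's wording; it is not a stated intention. A reader can also compare the proportional falls side by side, as the pilot's 54% and 69% allow, although no such comparison is planned.
- **The fall is not automatic for the count.** Each prevented flash takes 1 to 3 points off the score, but the moderate-to-severe count would not move if only mild flashes were prevented.
- **Mean rating per flash should not become the Objective 2 endpoint.** It conditions on flashes that still occur after randomization. Take 9/day with the 32/45/23% mix: the mean rating is 0.32 + 0.90 + 0.69 = 1.91 and the score 17.2/day. Prevent 1.8 mild flashes and nothing else: the score falls to 15.4, yet the mean rating rises to 15.4/7.2 = 2.14. The measure is also undefined for women whose flashes stop completely, who are the best responders.
- **The sizes are soft.** The 68% comes from 19 women recruited on 7 or more flashes a day, whereas this trial also requires 4 or more moderate-to-severe. Two pilot women stopped before the first outcome assessment, so the 68% and 46% may not describe the same women.

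What survives is the mismatch between the objective and its endpoints, and the absence of any measure that could separate the two effects.

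**Conclusion.** The point holds as a matter of interpretation: a positive result on the Objective 2 endpoints, as planned, supports a conclusion about frequency-weighted symptom burden and not about severity as such. Under an unchanged severity mix, the planned 1.8/day effect alone yields about 1.2/day on the count and 3.0 to 4.2 points/day on the score, close to the differences K.3 is powered for. Those sizes rest on the pilot share, an unknown moderate/severe split and a per-day reading of the score. The structural argument needs none of them.

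A reader might turn K.3 into a rate of false severity findings. Taking exactly 80% power gives standard errors of 1.5/2.80 = 0.54 and 3.3/2.80 = 1.18, and from these about 63% for the count and 73% to 95% for the score. K.3 says more than 80% and rounds its differences. These are also powers for true differences in the named endpoints, not false-positive rates, so the documents do not support that use.

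The primary endpoint, sample size and safety analyses are untouched. This is a cheap improvement to a secondary objective.

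**What to change.** Make these changes before treatment codes are broken:

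1. Reconcile Objective 2 (B.2 and K.1) with K.2.2. Describe the total score and the moderate-to-severe frequency as measures of frequency-weighted symptom burden, keep both, and limit the Objective 2 conclusion to burden.
2. In K.2.2, pre-specify two supportive analyses with the same baseline-adjusted mixed model: mean rating per recorded flash (score divided by count) and share of flashes rated moderate-to-severe. They do not replace the existing endpoints.
3. State that both are interpreted alongside total frequency, because they condition on flashes that still occur and can rise if mild flashes are prevented. Report by arm and visit the number of women with no flashes in the diary, for whom both are undefined. The entry criterion of 7 or more flashes per day means this cannot arise at baseline.
4. State the unit of the severity score in K.3 and align it with the 7-day sum in G.1.1.

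The cost is a few lines of text and two variables derived from diary data already collected. Nothing changes for participants, the sample size or the primary analysis.

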B. To evaluate the efficacy of uninterrupted transdermal NTG therapy in improving other symptom- and quality-of-life outcomes associated with hot flashes in peri- and postmenopausal women.

We hypothesize that, compared to placebo, uninterrupted use of NTG will result in significant improvements in sleep quality, anxiety and depression symptoms, and menopause-related quality of life over 12 weeks.

C. To examine the tolerability and safety of uninterrupted transdermal NTG therapy in peri- and postmenopausal women with hot flashes.

We hypothesize that, compared to placebo, uninterrupted use of NTG will be associated with higher rates of mild headache, but no significant differences in rates of chest pain, syncope, or severe adverse events defined by Common Terminology for Adverse Event Criteria severity grade 3 or higher.

C. BACKGROUND & RATIONALE

C.1 Background

Hot flashes (a.k.a. vasomotor symptoms) are the most common symptomatic complaint of menopausal women in the United States, with over two thirds reporting hot flashes at some point during the menopausal transition, and one in five reporting symptoms severe enough to require treatment (Gold, Sternfeld et al. 2000, Huang, Grady et al. 2008, Avis, Crawford et al. 2015). Although estrogen therapy is effective in suppressing hot flashes, it is associated with an increased risk of endometrial cancer, and when combined with a progestin to prevent endometrial hyperplasia, its long-term use can increase risk of coronary disease, thromboembolic events, and breast cancer (Rossouw, Anderson et al. 2002, Shumaker, Legault et al. 2003, Manson, Chlebowski et al. 2013).

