We will conduct a randomized, double-blinded, placebo-controlled trial to evaluate the efficacy and safety of continuous transdermal NTG for treatment of hot flashes. Peri- or postmenopausal women who report frequent hot flashes, are not using other clinical hot flash treatments, have no known history of coronary disease or multiple risk factors for coronary disease, and do not have contraindications to NTG therapy will be recruited from the San Francisco Bay area. Prior to randomization, women will be asked to record all hot flashes on a validated symptom diary over a 7-day period. They will then complete a brief, 3-day run-in period in which they will wear a 0.1 mg/hr transdermal NTG patch daily to confirm willingness to apply the patch and eliminate those with sensitivities to even low-dose NTG. Women who demonstrate an average of 7 or more hot flashes per day by their screening diaries, are successful in applying a 0.1 mg/hr patch daily during the run-in period, and meet all other eligibility criteria will then be randomized in equal ratios to daily use of transdermal NTG or placebo for 12 weeks.

Randomized participants will be started on a 0.2 mg/hr NTG (or identical-appearing placebo) patch daily, as the minimum dose previously found to produce at least a one-third decrease in hot flashes in the investigators' pilot study. Women will apply a new patch each night before going to bed, immediately after removing the old patch, and avoid patch-free periods that might interfere with development of tolerance. Women will return for follow-up at 1 week, and those who show no signs of hypotension or severe hypertension and are not already completely satisfied with the change in their symptoms will be increased to a 0.4 mg/hr NTG patch (or identical-appearing placebo) daily. Based on reassessment at 2 weeks, women may increase their NTG (or placebo) patch to 0.6 mg/hr for the remaining treatment period.

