Headache: Potential side effects of NTG therapy are related to the medication's vasodilatory action. The most commonly reported side effect is headache, occurring most frequently in the first 24 hours of administration (Tfelt-Hansen and Tfelt-Hansen 2009). In previous placebo-controlled trials of intermittent therapy with transdermal NTG (in which the NTG patch was removed at bedtime and replaced the next morning) at 0.2 to 0.8 mg/hr, approximately 60% of participants taking transdermal NTG reported headache, compared to 18% of participants taking placebo (Rossouw, Prentice et al. 2007). Among persons using continuous transdermal nitrate (immediately replacing the old patch with a new patch), development of tolerance to the vasodilatory effects of transdermal nitrate is expected within 12 to 24 hours, which should diminish the frequency and severity of headache. In the study team's prior pilot trial of continuous NTG for treatment of hot flashes in peri- and postmenopausal women, 37% of participants reported headache at some point during the 6-week study but the average duration of headache was less than 24 hours.

Lightheadedness/hypotension: Lightheadedness has been reported with initiation of NTG therapy, presumably due to lowering of blood pressure during the first 12 to 24 hours of administration. In prior placebo-controlled trials of intermittent NTG therapy for other indications, 6% of participants taking transdermal NTG reported transient lightheadedness thought to be associated with lowering of blood pressure, compared to 4% of participants taking placebo (Rossouw, Prentice et al. 2007). It is possible but uncommon for patients using transdermal NTG patches to develop hypotension severe enough to cause syncope. In the case of hypotension, removal of the transdermal patch should result in immediate (within seconds to minutes) normalization of blood pressure. Any lightheadedness or lowering of blood pressure associated with transdermal NTG therapy should

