To monitor participant safety, a clinical coordinator will assess for adverse events at each in-person or follow-up contact following initiation of study medication, starting with the Baseline Clinic visit. As noted in section I.3 below, coordinators will systematically and proactively assess for a pre-established set of severe side effects that are potentially attributable to NTG therapy. They will also encourage participants to volunteer information about other unanticipated adverse events by asking the standardized, open-ended question, "Have there been any changes in your health since your last visit?" Negative changes in health will be recorded as adverse events or serious adverse events on standardized forms as appropriate (see section I.3.1 below for definitions and documentation). Additionally, if participants contact clinical coordinators in between scheduled study visits and calls and report negative changes in their health, these will also be recorded as adverse events or serious adverse events.

I.3 Adverse Events and Serious Adverse Events

I.3.1 AE/SAE definitions

An Adverse Event (AE) is any untoward or unfavorable medical occurrence in a study participant, including any abnormal sign (e.g. abnormal physical exam or laboratory finding), symptom, or disease, temporally associated with the participants' involvement in the research, whether or not considered related to participation in the research. Medical conditions or diseases present before starting study interventions will only be considered adverse events if they worsen after starting the intervention.

A **Serious Adverse Event (SAE)** is any AE that results in death, is life threatening, or places the participant at immediate risk of death from the event as it occurred, requires or prolongs hospitalization, causes persistent or significant disability or incapacity, results in congenital anomalies or birth defects, or any other important event judged by the investigators to jeopardize the safety of a participant based upon appropriate medical judgment.

I.3.2 AE/SAE documentation

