At each follow-up visit or phone call after initiation of NTG or placebo, blinded study coordinators will systematically assess for the following severe side effects that could be attributable to NTG therapy: 1) headache severe enough to interfere with instrumental activities of daily living; 2) chest tightness or pain interfering with instrumental activities of daily living, and 3) syncope (fainting or loss of consciousness). If reported, these symptoms will be recorded on standardized SAE or AE forms, depending on whether they meet the threshold for being an SAE or a non-serious AE. These standardized SAE and AE forms will indicate date of onset, date of resolution, likelihood of relationship to treatment, and actions taken in response to the event.

To collect information about other or unanticipated adverse events, participants will also be asked about any other negative changes in their health at each telephone and in-person follow-up contact after initiation of therapy, using the standardized question, "Have there been any changes in your health since your last visit or call?" Participants will also be given telephone numbers to call study staff in between scheduled study visits or calls if they wish to report any health changes in between scheduled study visits or calls. Any negative changes in health that are reported will again be recorded as AEs or SAEs using standardized forms, as appropriate.

Additionally, using the Common Terminology Criteria for Adverse Events (CTCAE) system, all adverse events will be graded in severity using the 5-point CTCAE scale. According to this scale, AEs are considered grade 1 if they represent only mild symptoms or asymptomatic laboratory findings; grade 2 if they cause moderate symptoms that limit instrumental activities of daily living (shopping, transportation, household tasks); grade 3 if they are serious or disabling events or result in hospitalization or prolongation of hospitalization without being directly life-threatening; grade 4 if they are life-threatening events in which the participant is at risk of death at the time of the event if immediate intervention is not undertaken; or grade 5 if they are fatal adverse events.

I.3.3 AE/SAE reporting procedures

A. SAE reporting

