To assess tolerability and safety of NTG, we will compare group-specific rates of: 1) severe symptoms that are potentially attributable to NTG therapy (i.e., headache limiting activities of daily living, chest pain or tightness limiting activities of daily living, or syncope/fainting); and 2) any adverse events with a severity rating of 3 or higher on the CTCAE severity scale (National Cancer Institute 2009). We will also examine group-specific rates of all adverse events, regardless of severity and of anticipated relationship to NTG therapy. Inferences for rare outcomes will be obtained using Fisher's exact test. Because intention-to-treat analysis is conservative, any suggestive differences in safety outcome rates will be assessed accounting for adherence, final dose, and their interactions with treatment.

K.3 Sample Size Determination

Sample size calculations are based on parameter estimates from prior pharmacologic hot flash trials conducted by the investigators such as the FAST(Grady, Cohen et al. 2007) and CHIMES trials (Grady, Sawaya et al. 2009), which had similar eligibility criteria with respect to age, hot flashes, and treatment history. We assume the study sample will be characterized by: a) mean baseline hot flash frequency of >9 hot flashes/day; b) mean reduction in hot flash frequency in the control group of <3 hot flashes/day (i.e., <33%); c) standard deviation of change in hot flash frequency of ~4.5 hot flashes per day; and d) correlation between baseline and follow-up values of ~0.55.

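### Hypothesis 4 predicts more mild headache on NTG in the first 24 hours of therapy, but mild headache is recorded only if volunteered, no analysis is named for it, and the run-in alters the contrast, so the test is weak

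*Combined protocol and SAP*

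**What the plan says.** - **The hypothesis.** K.1 lists Hypothesis 4 among those the design is meant to test. It reads "Compared to placebo, uninterrupted use of NTG will be associated with higher rates of mild" "headache during the first 24 hours of therapy". B.2, objective C, gives the same prediction without a time limit: "uninterrupted use of NTG will be associated with higher rates of mild headache, but no significant differences in rates of chest pain". Neither place says whether therapy starts with the run-in patch or with the first randomised patch.
- **The run-in.** Section D, on all women before randomisation: "They will then complete a brief, 3-day run-in period in which they will wear a 0.1 mg/hr transdermal NTG patch daily". Under I.1.2 (Headache), women who develop significant headache in this period are excluded. Randomised treatment then starts at 0.2 mg/hr NTG or placebo (F.1.6).
- **When headache is expected.** I.1.1 describes NTG headache as "occurring most frequently in the first 24 hours of administration" and expects tolerance within 12 to 24 hours of continuous use.
- **What is asked.** G.1.3 B and I.3.2 have coordinators ask specifically about "headache severe enough to interfere with instrumental activities of daily living". Anything else depends on an open question about changes in health (G.1.3 C, I.3.2). Events are graded and their dates of onset and resolution recorded.
- **When it is asked.** I.2 has adverse events assessed "following initiation of study medication, starting with the Baseline Clinic visit". The next visit is 4 to 10 days later (H.2.8).
- **What is compared.** K.2.4 compares "headache limiting activities of daily living, chest pain or tightness limiting activities of daily living, or syncope/fainting", then events of grade 3 or higher, then all adverse events regardless of severity.

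**The concern.** Headache is the side effect the protocol expects most often, and more mild headache is the only difference between arms that Hypothesis 4 predicts. Yet the direct question starts above the mild grade, no analysis is attached to the prediction, and the period of highest expected risk comes before randomisation. A small or null difference could then reflect incomplete recording, or the selection of women who had already tolerated NTG, and still be read as evidence that early headache is not a problem. The primary efficacy result is not affected.

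**Working it through.** The plan gives no power or expected rate for Hypothesis 4, so there is no figure to reproduce. The check compares the hypothesis with the design, then illustrates what incomplete reporting costs.

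**1. Severity.** On the scale in I.3.2, an event that limits instrumental activities is grade 2, and mild symptoms are grade 1. The direct question therefore starts at grade 2. Mild headache falls below it and reaches the database only through the open question.

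**2. Timing.** The first contact after randomisation is at day 4 to 10, so symptoms in the first 24 hours are recalled several days later. Patches are applied at night (H.1.4 B), so the first 24 hours span two calendar dates. The adverse event forms are described as recording dates, with no mention of clock times. A 24-hour window cannot be cut exactly from such data.

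**3. Exposure.** There are two possible starts of therapy:

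| If therapy starts with | First 24 hours | Placebo group in that window? |
|---|---|---|
| the first run-in patch | 0.1 mg/hr NTG, all women | no |
| the first randomised patch | 0.2 mg/hr NTG or placebo, 1:1 | yes, in women already exposed to NTG and selected for tolerating it |

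Only the second start gives a randomised comparison. It does not cover a woman's first exposure to NTG, which is when I.1.1 expects most headache.

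**4. Analysis.** K.2.4 names activity-limiting headache, chest pain or tightness, syncope, and events of grade 3 or higher. Mild headache enters only within all adverse events. No time window is given, and nothing says whether events from the run-in, collected at the Baseline visit, are kept out of the comparison by arm.

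**5. Cost of incomplete reporting.** Let p1 and p0 be the true proportions with headache on NTG and on placebo, and f the share of headaches volunteered, assumed equal in both arms. The recorded proportions are f × p1 and f × p0. The recorded difference is f × (p1 − p0), so it shrinks in proportion to f.

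Inputs: 70 per arm and two-sided 5% (K.3); Fisher's exact test, which K.2.4 gives for rare outcomes; power by full enumeration of two binomials, with no allowance for dropout. There are two scenarios: 30% versus 10%, which is assumed, and 60% versus 18%, which I.1.1 cites for any headache in placebo-controlled trials of intermittent NTG. The values of f are assumptions.

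| True rates | f | Recorded rates | Difference (points) | Power |
|---|---|---|---|---|
| 30% vs 10% | 1 | 30% vs 10% | 20 | 81% |
| 30% vs 10% | 0.5 | 15% vs 5% | 10 | 41% |
| 30% vs 10% | 0.25 | 7.5% vs 2.5% | 5 | 13% |
| 60% vs 18% | 1 | 60% vs 18% | 42 | over 99% |
| 60% vs 18% | 0.5 | 30% vs 9% | 21 | 86% |
| 60% vs 18% | 0.25 | 15% vs 4.5% | 10.5 | 46% |

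**The case against.** The strongest reply is that the hypothesis compares NTG with placebo, and placebo exists only after randomisation. On that reading, therapy means randomised therapy, and its first 24 hours are a valid contrast at twice the run-in dose. A patch-free gap before randomisation is also possible, because H.1.3 sets only a minimum of 10 days between the screening and baseline visits. The open question is asked at every contact, every event is graded and dated, and K.2.4 will examine all adverse events by group. Mild headache is not among the safety outcomes in G.2, and the run-in is a disclosed choice with a stated purpose.

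Much of this stands, and it rules out several stronger readings that a reader might reach:

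- *Both arms spend the first 24 hours of therapy on active NTG.* This is true only if therapy starts at the run-in, which the documents do not say.
- *Mild headache is never elicited.* It is not systematically elicited. The open question can pick it up.
- *The trial cannot test the hypothesis.* A randomised contrast and a route for recording mild headache both exist. At the cited 60% versus 18%, power stays at 86% even if only half of headaches are volunteered.
- *Run-in events will be counted by arm.* K.2.4 does not exclude them, but no section says they will be counted, and onset dates would allow them to be separated.

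The reply leaves four things unanswered: the direct question starts above the mild grade, K.2.4 names no matching comparison, K.1 and B.2 differ on the window, and the start of therapy is undefined.

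**Conclusion.** The concern holds as a weak and under-specified test. Hypothesis 4 has no systematic measurement at the grade it names, no named analysis, and two wordings of its time frame. The contrast that remains is 0.2 mg/hr NTG versus placebo in women who have already worn NTG for 3 days without significant headache, so it says little about headache at first exposure.

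The loss from passive reporting could be small or large. Across the two scenarios, power runs from 86% down to 41% if half of headaches are volunteered, and from 46% down to 13% if a quarter are. These are illustrations. The 30% versus 10% pair is assumed, and the 60% versus 18% pair covers headache of any severity under intermittent use. Neither is a first-24-hour rate of mild headache, and the documents do not give the share volunteered. The calculation assumes equal reporting in both arms and leaves out any effect of run-in selection. The direction is firmer than the size: under-reporting that is equal in both arms narrows the absolute difference. The primary outcome and the safety outcomes listed in G.2 do not depend on this point.

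**What to change.** - **Ask directly.** Add one item to the existing adverse event form, *any headache since last contact (onset date, severity)*, at the Baseline visit (covering the run-in) and at each contact after randomisation.
- **Name the comparison.** In K.2.4, add a comparison by arm of any-grade headache and of mild headache with onset after the first randomised patch. Report run-in headache separately, as uncontrolled data on active NTG.
- **Define the start.** State in K.1 and B.2 that therapy begins with the first randomised patch, in women who completed the run-in. Give the 24-hour window in both places or drop it from K.1. If it is kept, the form needs time of onset as well as date.

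The cost is one question on a form already in use and wording in B.2, K.1 and K.2.4. The downside is that direct questioning raises headache counts in both arms, so the rates will not be comparable with those from studies that relied on open reporting. Nothing here changes the treatment, the run-in or eligibility.
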